3.3.3 Treatments Administered

3.3.3.1 Product Description

The P2-VP8 subunit rotavirus vaccine is made by inserting a codon optimized synthetic gene encoding the VP8 region of rotavirus VP4 fused to the P2 T-cell epitope coding sequence of tetanus toxin into the Pj411 proprietary cloning vector developed by DNA 2.0, Menlo Park, CA. The vector carries a kanamycin resistance gene as a selection marker. The vector was transfected into the BL21 strain of *E. coli*. The fusion protein is purified from Isopropyl β -D-1-thiogalactopyranoside (IPTG)-induced and physically lysed cultures using standard column chromatographic techniques employing Q-Sepharose and Butyl 650 as resins in addition to ultrafiltration and diafiltration. The purified protein is co-formulated with aluminum hydroxide $[\text{Al}(\text{OH})_3]$.

3.3.3.2 Presentation and Formulation

The trivalent P2-VP8 vaccine is formulated as a sterile suspension containing a total of 360 μg of protein (120 μg of each P type) per mL adsorbed to aluminum hydroxide (1.125 mg of aluminum per mL in a phosphate buffer, pH 7). The vaccine is contained within a 2 mL borosilicate glass vial sealed with a butyl rubber stopper and a crimped metal collar. The vaccine is stored at 2-8°C. To produce the 15, 30 and 90 μg doses (containing 5, 10 and 30 μg of each P2-VP8 vaccine component, respectively), the vaccine is diluted with the aluminum hydroxide adjuvant diluent within 6 hours of administration (aluminum hydroxide diluted to a concentration of 1.125 mg/mL before being used to dilute the vaccine).

The doses of the trivalent P2-VP8 subunit vaccine will be prepared in the pharmacy. Blinded study syringes will be prepared for the study coordinator for administration to the volunteers

3.3.4 Method of Assigning Participants to Treatment Groups (Randomization)

Enrollment is sequential in the order given below and in the group sample sizes given in Table 3.3.4.

Cohort A1: Adults were randomly assigned to 30 µg P2-VP8 or Placebo in a 4:1 ratio.

Cohort A2: Adults were randomly assigned to 90 µg P2-VP8 or Placebo in a 4:1 ratio.

Cohort B1: Toddlers were randomly assigned to 30 µg P2-VP8 or Placebo in a 4:1 ratio.

Cohort B2: Toddlers were randomly assigned to 90 µg P2-VP8 or Placebo in a 4:1 ratio.

Cohort C1: Infants were randomly assigned to 15 µg P2-VP8 or Placebo in a 3:1 ratio.

Cohort C2: Infants were randomly assigned to 30 µg P2-VP8 or Placebo in a 3:1 ratio.

Cohort C3: Infants were randomly assigned to 90 µg P2-VP8 or Placebo in a 3:1 ratio.

Cohort D: Infants were randomly assigned to 15 µg, 30 µg or 90 µg of P2-VP8, or to Placebo in a 1:1:1:1 ratio.

Table 3.3.4 Dosing Schedule

Group	P2-VP8 dose	N	Study Day		
			0	28	56
A Adults	30 µg	12	X	X	X
	Placebo	3	X	X	X
	90 µg	12	X	X	X
	Placebo	3	X	X	X
B Toddlers	30 µg	12	X		
	Placebo	3	X		
	90 µg	12	X		
	Placebo	3	X		
C Infants	15 µg	12	X	X	X
	Placebo	4	X	X	X
	30 µg	12	X	X	X
	Placebo	4	X	X	X
	90 µg	12	X	X	X
	Placebo	4	X	X	X
D Infants	15 µg*	138	X	X	X
	30 µg*	138	X	X	X
	90 µg*	138	X	X	X
	Placebo	138	X	X	X

X = Injection day

* If dose tolerated in Group C

3.3.5 Blinding

The randomization scheme was generated and maintained by the Statistical Data Coordinating Center (SDCC) at the Emmes Corporation, Rockville, MD. Randomization and assignment of treatment codes is performed using the enrollment module of the Emmes AdvantageEDCSM electronic data capture system on the day participants received their first study vaccination, after confirmation of eligibility and immediately prior to immunization. The blinded investigator provides the treatment assignment code to the unblinded study pharmacist or member of the IP formulation team for preparation of the vaccine or placebo to be given to the participant. The unblinded pharmacist refers to a Treatment Key Listing, provided for the trial by Emmes, to determine the treatment for the participant. The pharmacist maintains the Treatment Key Listing under locked/secured conditions and does not reveal the randomization code to any other study staff member, participant or parent. Investigational study product was prepared by a qualified unblinded research pharmacist and witnessed by another unblinded study staff member then dispensed in a masked syringe (opaque sheath over the syringe barrel) with administration needle. All follow-up safety and efficacy evaluations are performed by blinded clinic staff.

3.4 Immunogenicity and Safety Variables

The following section describes the collection of immunogenicity and safety variables. For a detailed schedule of activities refer to Table 14.1.3 of the protocol. For a list of the primary and secondary immunogenicity and safety variables, refer to Section 2.2 of this report.

3.4.1 Safety Variables

The safety variables to be assessed are unsolicited adverse events (AEs), serious adverse events (SAEs), multiple clinical safety laboratory measurements [including white blood cells (WBC), hemoglobin (Hgb), platelets, alanine aminotransferase (ALT), albumin, total bilirubin and serum creatinine], physical exam, and vital sign parameters. Solicited systemic reactogenicity events within 7 days of each vaccination are also collected. If a solicited sign or symptom starts during the seven days post-vaccination and continues, it is still reported as a reactogenicity symptom. Any symptom starting after seven days post-vaccination is recorded as an AE. Safety events are collected from the time of the first study injection through completion of the study at 6 months after the final injection (as above). For participants who withdraw or were withdrawn from the study, an early termination visit should occur 5-7 days after the last injection or study visit to elicit occurrence of AEs (serious and non-serious).

3.4.1.1 Reactogenicity Events

Reactogenicity events are adverse events that are common and known to occur or are of particular interest following the administration of the study vaccine. These events are collected in a standard, systematic format using a graded scale based on functional assessment or magnitude of reaction. The reactogenicity adverse events are solicited systemic reactions collected by interviews with the participant/parent/guardian, memory aids and assessed by the site at clinic visits. Reactogenicity assessments include the following:

Local reactogenicity (adults, toddlers and infants)

- Pain
- Tenderness
- Erythema
- Induration
- Pruritus

Systemic Reactogenicity (Adults)

- Fever
- Headache
- Vomiting
- Nausea
- Fatigue
- Chills
- Myalgia

Systemic Reactogenicity (Toddlers and infants)

- Fever
- Vomiting
- Irritability
- Decreased activity
- Decreased appetite

3.4.1.2 Unsolicited Adverse Events

An AE is defined as any untoward medical occurrence associated with the use of a vaccine in humans, whether or not considered vaccine related, that occurs during the conduct of a clinical trial. Any change from baseline assessment of clinical status, routine laboratory tests, X-rays, physical examinations, etc., that is considered clinically significant by the PI is considered an AE.

AEs, including non-solicited injection site and systemic reactions not meeting the criteria for "SAEs" were captured on the appropriate case report forms. All AEs are followed until resolution or stability. AEs are graded for severity and relationship to study product. AEs are also coded by MedDRA® version 19.1 or higher for preferred term and system organ class.

The study site assigns severity grades based on the severity grading criteria provided in Appendix II of the Protocol. Possible grades are from Mild (Grade 1) to Life Threatening (Grade 4). Any AEs leading to death are Grade 5 events. AEs are graded with the most severe grade during the illness/symptom.

When assessing causality of an AE to study product, the PI considers whether there was a reasonable possibility that the study product caused the event. Reasonable possibility implies there is evidence to suggest that the study product caused the reported event. An affirmative answer designates the event as a suspected adverse reaction, and the AE is considered "related". If the answer is no, then the AE is considered "unrelated".

3.4.1.3 Serious Adverse Events

An SAE, including a serious suspected adverse reaction or serious adverse reaction as determined by the PI or the Sponsor, is any event that results in any of the following outcomes:

- Death;
- Life-threatening adverse event (Life-threatening means that the study participant was, in the opinion of the PI or Sponsor, at immediate risk of death from the event as it occurred);
- Inpatient hospitalization greater than 24 hours or prolongation of existing hospitalization;

- Persistent or significant incapacity or substantial disruption of the ability to conduct normal life function, or;
- Congenital abnormality or birth defect;
- Important medical events that may not result in one of the above outcomes but may jeopardize the health of the study participant or require medical or surgical intervention to prevent one of the outcomes listed in the above definition of serious event.

All SAEs are:

- Recorded on a multi-page SAE form set and sent to the Emmes Coordination Center within 24 hours of the site's knowledge of the event.
- Reviewed by the Emmes Medical Monitor and a report written and provided to the PI.
- The site PIs ensure the timely dissemination of required SAE information, including expedited reports, to their respective local ethics committees in compliance with applicable local regulations and guidelines and are responsible for submitting the safety report (initial and follow up SAE reports) or other safety information (e.g., revised IB) to their respective ethics committees and for retaining a copy in the site's study file.
- The Emmes Coordinating Center notifies the Sponsor and the CRO performing site monitoring simultaneously with the reporting to the clinical database. They also provide the SRC, the PATH Medical Officer and the Emmes Medical Monitor with listings of all SAEs on an ongoing basis.
- Reviewed by the site PI who applies clinical judgment to determine whether the SAE is of sufficient severity to require discontinuation of administration of study injection for that participant. If necessary, the site PI will suspend any trial procedures and institute the necessary medical therapy to protect the participant from any immediate danger.
- Followed to resolution by the PI or a study physician.
- Reported to the WIRB by PVS according to the WIRB guidelines and using the WIRB Ten Day Adverse Event Form.

SAEs are collected on each subject through 6 months after the final study vaccination.

3.4.2 Immunogenicity Variables

Antibody (IgG and IgA by ELISA) to P2-VP8 and Rotavirus neutralization analyses will be performed on sera from the following visits:

		4 Weeks Post Vac.1 Day 28	4 Weeks Post Vac.2 Day 56	4 Weeks Post Vac.3 Day 84
	Screening			
Adults:	X	X	X	X
Toddlers:	X	X		
Infants:	X		X	X

Anti-rotavirus IgA (whole viral lysate) by ELISA will be determined in serum samples collected at baseline and one month after the final study injection (i.e., day 84).

Additional immunogenicity assays may be performed by research laboratories to further evaluate post-study injection immune responses and to explore whether correlates of protection may be identified

For immunogenicity variables, data inferior to the Lower Limit of Quantification (LLOQ) will be replaced by half the detection limit; data superior to the Upper Limit of Quantification (ULOQ) will be replaced by the limit (truncated data). No search for outliers will be performed. Prior to statistical analysis, all immunology data will be \log_{10} transformed to improve the distributional properties of the data and reduce the impact of potential outliers.

4 SAMPLE SIZE CONSIDERATIONS

4.1.1 Primary Safety Endpoints

Safety will be assessed by analyses of the following primary endpoints (events), where the unit of analysis in each case will be the proportion of participants with at least one event:

- Moderate or greater solicited local reactions
- Moderate or greater solicited systemic reactions
- Moderate or greater adverse events
- Moderate or greater adverse events where there is a reasonable possibility that the study product caused the event, i.e., are suspected adverse reactions
- Serious adverse events

It was assumed that almost all participants enrolled would provide data for safety analysis and at least 90% of enrolled participants would be evaluable for immunogenicity assessments.

Safety

The sample size for this study was selected to detect frequent adverse events. Given a planned sample size of 12 vaccine recipients per dose group and 24 vaccine recipients for the two dose groups combined in both adults and toddlers (A and B), the study will have an approximately 90% chance of observing at least one AE that occurs at a rate of 17.5% and 9.2%, respectively. For the two infant cohorts combined (C and D), 150 vaccine recipients per dose group and 450 vaccine recipients for the three dose groups combined will provide at least 90% chance of observing an AE that has a 1.6% and 0.5% rate of occurrence, respectively.

Conversely, if no SAEs are observed in 24 and 450 vaccine recipients, the study will be able to rule out SAEs occurring at a rate of approximately 11.7% and 0.7%, respectively based on the upper bounds of the one-sided 95% confidence.

Primary Immunogenicity Endpoints

Based on the results in South African infants who received monovalent P2-VP8 vaccine or placebo (VAC-013), the strain specific seroresponse rates for both P2-VP8 vaccine doses were expected to be $\geq 80\%$ for at least one of the three P2-VP8 vaccine doses and $<20\%$ for the placebo group. For the two infant cohorts combined, with 135 evaluable recipients per dose level (assuming 10% loss), this study was designed to provide at least 74% and 95% power (Fisher's exact 2-tailed test) to detect 15 and 20 percentage points

difference (e.g. 65% vs. 80% and 60% vs. 80%), respectively, in seroresponse rates between any two P2-VP8 dose groups. For comparisons with the combined placebo groups, this study was designed to provide $\geq 99\%$ power (Fisher's exact 1-tailed test) to detect a ≥ 30 percentage point increase in the P2-VP8 group compared with placebo (e.g. 50% vs. 20%).

For the sample calculations of the Geometric Mean Titer (GMT) endpoint based on the VAC 013 study, the LOG_{10} standard deviations were estimated to be <0.6 (range: 0.24 – 0.56) for the P2-VP8 doses and the placebo group. Using a conservative LOG_{10} standard deviation (SD) of 0.6, this study with 135 evaluable infants per group (assuming 10% loss) was designed to provide at least 98% power to detect as low as a 2-fold difference between any two P2-VP8 dose groups or between any P2-VP8 vaccine dose (15 μg , 30 μg or 90 μg dose) and the placebo group.

i.e., for 2 groups A & B, with A > B:

$$\text{Require } \text{GMT(A)} / \text{GMT(B)} \geq 2$$

$$\text{i.e., } \text{Log}_{10}\text{A} - \text{Log}_{10}\text{B} \geq \text{Log}_{10}(2) \approx 0.301$$

$$\text{Therefore, } \text{A} \sim \text{N}(\mu, 0.6) \text{ and } \text{B} \sim \text{N}(\mu - 0.301, 0.6)$$

Under this assumption using a student t-test, a sample size of N=135 (per group) will give 98% power to detect a significant difference at the 5% level in mean Log_{10} titer between 2 groups of at least 0.301.

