3 INVESTIGATIONAL PLAN

3.1 Overall Study Design and Plan

The trial is a double-blind, randomized, placebo-controlled dose-escalation study in which two dose-levels (30 µg and 90 µg) of vaccine will be tested in adults and toddlers and then three dose-levels will be assessed in infants (15 µg, 30 µg and 90 µg).

In **Group A**, cohorts of 15 adults (12 vaccine and 3 placebo recipients) per dose level will receive three study injections at 4 week intervals (consistent with the regimen in the adult study of the monovalent vaccine), advancing from the first to the second dose-level after assessment of safety data through the first week after the first injection (A1).

Based on the safety data in the adult group, **Group B** cohorts of 15 toddlers (12 vaccine recipients and 3 placebo recipients) per dose level will receive a single intramuscular injection (consistent with the regimen administered to toddlers in the current study of the monovalent vaccine in toddlers), advancing from the first to the second dose-level after assessment of safety data through the first week after the injection in the lower dose toddler group (B1) and all available data for the adult group.

Based on the safety data in group B toddler cohorts, **Group C** cohorts of 16 infants (12 vaccine recipients and 4 placebo recipients) per dose level will receive three study injections at 4 week intervals (concomitant with EPI vaccinations, with the exception of rotavirus vaccination), starting at ≥ 6 and < 8 weeks of age. Advancing from the first to the second dose-level in Group C will occur after assessment of safety data through the first week after the first injection (C1), as well as all available data for toddlers and adults. Advancing from the second to the third dose-level (90 µg) in Group C will occur after assessment of safety data through the first week after the first injection of the second dose-level (30 µg).

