3.2 STUDY SCHEMA

Group		Trivalent P2-VP8 Dose	N	-7 ^a to -1	0	7	28	56	84	89, 91, 93	168	224
A Adult	A1	30 µg	12	B(S,I)	X	B(S)	X, B(I)	X, B(I)	B(I)			F
		Placebo	3	B(S,I)	P	B(S)	P, B(I)	P, B(I)	B(I)			F
	A2	90 µg	12	B(S,I)	X	B(S)	X, B(I)	X, B(I)	B(I)			F
		Placebo	3	B(S,I)	P	B(S)	P, B(I)	P, B(I)	B(I)			F
A Total			30									
B Toddler	B1	30 µg	12	B(S,I)	X	B(S)	B(I)				F	
		Placebo	3	B(S,I)	P	B(S)	B(I)				F	
	B2	90 µg	12	B(S,I)	X	B(S)	B(I)				F	
		Placebo	3	B(S,I)	P	B(S)	B(I)				F	
B Total			30									
C Infant	C1	15 µg	12	B(S,I)	X	B(S)	X	X, B(I)	B(I)	Sh		F
		Placebo	4	B(S,I)	P	B(S)	P	P, B(I)	B(I)	Sh		F
	C2	30 µg	12	B(S,I)	X	B(S)	X	X, B(I)	B(I)	Sh		F
		Placebo	4	B(S,I)	P	B(S)	P	P, B(I)	B(I)	Sh		F
	C3	90 µg	12	B(S,I)	X	B(S)	X	X, B(I)	B(I)	Sh		F
		Placebo	4	B(S,I)	P	B(S)	P	P, B(I)	B(I)	Sh		F
C Total			48									
D Infant		15 µg	138	B(S,I)	X		X	X, B(I)	B(I)	Sh		F
		30 µg	138	B(S,I)	X		X	X, B(I)	B(I)	Sh		F
		90 µg	138	B(S,I)	X		X	X, B(I)	B(I)	Sh		F
		Placebo	138	B(S,I)	P		P	P, B(I)	B(I)	Sh		F
D Total			552									
All Cohorts Total			660									

X = Trivalent P2-VP8 vaccine

P = placebo

B = blood sample for (S) safety and/or (I) immunogenicity testing

F = final study f/u visit/call

Sh = stool samples to assess Rotarix shedding. Only at RMPRU (Soweto).

^aFor adult and toddler cohorts, -28 to -1

For each age group, progression from one dose level to the next will require review of clinical and safety lab data through 7 days after the first dose at the lower dose level. Safety laboratory blood specimens will be drawn at baseline for all participants (screening) and 7 days after first study injection in Groups A, B and C.

[figure not shown]
Blood samples for immunogenicity analysis will be obtained at baseline for all participants, Days 28, 56 and 84 for Group A (adults), Day 28 for Group B (toddlers), and Days 56 and 84 for Groups C and D (infants).

Stool samples to assess Rotarix shedding will be obtained from infants (Groups C and D) on days 89, 91 and 93 (i.e., 5, 7 and 9 days after the first Rotarix dose on day 84) in the subset of infants enrolled at the Respiratory and Meningeal Pathogens Research Unit (RMPRU).

For each dose level, progression from adults in Group A to toddlers in Group B and then to infants in Group C will require review of clinical and safety laboratory data through 7 days after study injection in the older group. (see Figure 1)

These determinations will be made by the Safety Review Committee (SRC).

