5.7 Multicenter Studies

This study is being conducted at 3 sites: the Respiratory and Meningeal Pathogens Research Unit (RMPRU) in Soweto enrolled all participants in groups A to C. Group D infants were enrolled at 3 sites: RMPRU, SRC (Shandukani Research Centre) and FAM-CRU (Family Clinical Research Unit, Tygerberg). All summary tables, graphs and listings for infants in groups C and D will be reported by site and for all 3 sites combined.

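### The infant AE detection limits of 1.6% and 0.5% do not hold for laboratory AEs found only on scheduled bloods, which rest on 12 infants per dose and 36 in all

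*SAP*

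**What the plan says.** Section 4.1.1 justifies the infant sample size for safety with Groups C and D combined: "150 vaccine recipients per dose group and 450 vaccine recipients for the three dose groups combined will provide at least 90% chance of observing an" adverse event, the rates being given as "observing an AE that has a 1.6% and 0.5% rate of occurrence, respectively". It makes no exception by type of AE, and it assumes that nearly all enrolled participants will contribute safety data.

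Three other places bear on what can be seen in those infants.

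- **Laboratory changes can be AEs.** Section 3.4.1.2: "Any change from baseline assessment of clinical status, routine laboratory tests, X-rays, physical examinations, etc., that is considered clinically significant by the PI is considered" to be an adverse event. Section 2.3.1 says much the same. Section 3.4.1 lists WBC, haemoglobin, platelets, ALT, albumin, bilirubin and creatinine as safety variables, without limiting them to particular groups.
- **Safety bloods.** Section 3.2: "Safety laboratory blood specimens will be drawn at baseline for all participants (screening) and 7 days after first study injection in Groups A, B and" Group C. In the schema, the Group D rows show a baseline safety draw and nothing on Day 7.
- **Reporting.** Section 5.1 bases percentages for categorical measures on the population size. Section 5.7: "All summary tables, graphs and listings for infants in groups C and D will be reported by site and for all 3 sites combined". Section 7.1.1 tabulates AEs by study cohort and product received. Section 7.1.3 summarises laboratory changes to one week after vaccination separately and descriptively.

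**The concern.** One detection limit is stated for all infant AEs, but one class of AE is not looked for in most of the infants behind it. A laboratory abnormality without symptoms comes to light only if blood is drawn, and for 92% of vaccinated infants (138 of 150 per dose) none is scheduled after injection.

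Two things follow. The stated sensitivity is not delivered for this class of AE. And if such events are expressed over the full infant population, infants who were never sampled count as free of them. All of Group C was enrolled at one site (section 5.7), so in by-site tables scheduled bloods can produce laboratory AEs at that site only.

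Sections 5.8 and 7 say that safety results will enter the Phase 3 dose selection. A combined infant table with no liver, haematology or creatinine AEs could be taken as evidence from 450 vaccinees. As far as scheduled testing goes, it would rest on 36 infants sampled once, after the first of three injections.

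**Working it through.** **Inputs**

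- Group C: "cohorts of 16 infants (12 vaccine recipients and 4 placebo recipients) per dose level", so 12 vaccinees per dose and 3 × 12 = 36 in all; placebo 3 × 4 = 12 (section 3.1).
- Group D: 138 in each of four arms (section 3.1).
- Combined: 12 + 138 = 150 per dose; 3 × 150 = 450 vaccinees; placebo 12 + 138 = 150.
- Post-injection safety blood: Group C only among infants (section 3.2).

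**Formulas**

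- Chance of at least one event: 1 − (1 − p)^n
- Rate seen at least once with 90% chance: 1 − 0.1^(1/n)
- One-sided 95% upper bound after zero events: 1 − 0.05^(1/n)

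**The plan's own figures**

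| n | Stated rate | Chance of at least one event |
|---|---|---|
| 12 | 17.5% | 90.1% |
| 24 | 9.2% | 90.1% |
| 150 | 1.6% | 91.1% |
| 450 | 0.5% | 89.5% |

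The last row falls just under 90% through rounding, since the exact rate for n=450 is 0.51%. The zero-event bounds for SAEs also reproduce: 11.7% for n=24 and 0.66% (stated as 0.7%) for n=450. The plan's arithmetic is sound.

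**AEs visible only on the scheduled Day 7 blood**

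| | Per dose | All doses |
|---|---|---|
| Infants sampled | 12 | 36 |
| Chance of at least one event at the plan's rate | 1 − 0.984^12 = 17.6% (at 1.6%) | 1 − 0.995^36 = 16.5% (at 0.5%) |
| Rate detectable with 90% chance | 1 − 0.1^(1/12) = 17.5% | 1 − 0.1^(1/36) = 6.2% |
| Upper bound after zero events | 1 − 0.05^(1/12) = 22.1% | 1 − 0.05^(1/36) = 8.0% |

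The per-dose figure agrees with what section 4.1.1 already gives for 12 adults or toddlers: "approximately 90% chance of observing at least one AE that occurs at a rate of 17.5% and 9.2%, respectively" for 12 and 24 recipients.

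**Dilution of a combined C and D percentage**

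Let f be the fraction of these AEs that Group D would still find through clinically indicated testing. The combined rate is too low by the factor 150 / (12 + 138f). The plan gives no value for f, so the values below are assumptions.

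| f | Factor |
|---|---|
| 0 | 12.5 |
| 5% | 7.9 |
| 10% | 5.8 |
| 25% | 3.2 |
| 50% | 1.9 |

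As an illustration at f = 0, one event gives 1/12 = 8.3% (exact 95% CI 0.2% to 38.5%) over the infants sampled, and 1/150 = 0.7% (0.02% to 3.7%) over the combined group.

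**Between-arm comparison**

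The sampled fraction is 12/150 = 8% in each vaccine arm and 12/150 = 8% in placebo, so the loss of ascertainment is the same in every arm.

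**The case against.** The strongest case against the point has four parts.

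- **The figures are right for what they mainly describe.** Clinical AEs and SAEs are sought in every infant, and the primary safety endpoints in section 4.1.1 are reactions, AEs and SAEs, with no laboratory endpoint among them. A reader might infer that the plan has miscalculated, or that all its infant AE rates are about 12 times too low. Neither follows: the calculation reproduces, and only laboratory-detected AEs are affected. But a laboratory change that the investigator judges clinically significant is an AE under the plan, and can enter the AE endpoints of section 4.1.1. The missing limit of scope therefore stands.
- **A combined table may not be what is produced.** Section 7.1.1 tabulates by study cohort. Section 4.1.1 calls C and D the two infant cohorts, and section 3.3.4 lists C1 to C3 and D separately, so Group C may well appear on its own. This softens the harm. It does not remove it: section 5.7 also asks for infant results over all sites combined without saying whether C and D stay apart, and no section changes the denominator for laboratory AEs.
- **Laboratory safety has its own summary.** Section 7.1.3 covers changes to one week, and section 5.1 reports the non-missing n for continuous variables, so a careful reader will see how many were tested. This stands, but it does not correct the detection limit in section 4.1.1.
- **The largest figure is a ceiling.** The 12.5-fold factor needs a combined denominator and no detection at all in Group D. This stands in full.

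A reader might also infer that the site holding Group C will look less safe than the others. Only 48 infants there have the extra bleed and no between-site test is planned, so the plan supports saying only that ascertainment differs by site.

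**Conclusion.** The point holds as an error of scope. The limits of 1.6% (n=150) and 0.5% (n=450) are valid for AEs ascertained in every infant. For AEs seen only on scheduled safety bloods, the corresponding rates are about 17.5% per dose (n=12) and 6.2% overall (n=36), and at the plan's own rates the chance of seeing even one is 17.6% and 16.5% instead of about 90%.

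These replacement figures have a limit of their own. They apply to abnormalities present at one draw a week after the first injection, while the primary AE window in section 7.1.1 runs to 28 days after the last.

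Any combined C and D percentage for laboratory AEs over the full population would be too low by at most 12.5-fold, assuming that Group D finds none, and by less if clinically indicated tests find some. Comparisons between arms are not biased, and the zero-event statement for SAEs is untouched. What is affected is the stated sensitivity and the absolute rates for this one class of AE.

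**What to change.** 1. In section 4.1.1, limit the 1.6% and 0.5% figures to AEs ascertainable in all infants. Add that for laboratory abnormalities detectable at the single Day 7 Group C bleed, the rates seen at least once with 90% chance are about 17.5% per dose (n=12) and 6.2% for all doses (n=36).
2. In section 7.1.1, report AEs arising from scheduled safety bloods over the number of infants with a post-injection safety sample (Group C).
3. Footnote combined and by-site infant AE tables to say that Group D had no scheduled safety blood after injection.

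The cost is some SAP wording and one small table split, with no new data. The downside is a less favourable stated detection limit for laboratory AEs.

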1.1 Purpose of the Analyses

This Statistical Analysis Plan describes the statistical methodology and summaries required to assess the safety, tolerability and immunogenicity of 3 dose-levels of the trivalent P2-VP8 subunit rotavirus vaccine when administered to healthy South African toddlers and infants. The primary study hypotheses are as follows:

Safety

The trivalent P2-VP8 subunit rotavirus vaccine is safe and well-tolerated in healthy South African adults, toddlers and infants.

Immunogenicity

The trivalent P2-VP8 subunit rotavirus vaccine is immunogenic in healthy South African infants and will induce neutralizing immune responses to at least 2 of the 3 strains from which vaccine antigens are derived in 60% or more of participants in at least one of the study groups

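### The stated 74% and 95% power for dose comparisons is not a floor for any two doses, and the 95% is 93.9% at the plan's own example rates

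*SAP*

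**What the plan says.** The statement is in SAP section 4.1.1, under the sub-heading on primary immunogenicity endpoints. It promises "at least 74% and 95% power (Fisher's exact 2-tailed test) to detect 15 and 20 percentage points" and continues with "difference (e.g. 65% vs. 80% and 60% vs. 80%), respectively". The scope is given as "in seroresponse rates between any two P2-VP8 dose groups". The sample size behind it is described as "with 135 evaluable recipients per dose level (assuming 10% loss".

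The preceding sentence sets the planning premise. From the monovalent study in South African infants, strain-specific seroresponse is expected to be 80% or higher for one or more of the three doses and below 20% on placebo. No rate is given for the other two doses.

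**The concern.** For a fixed difference between two proportions, power depends on where the two rates lie. It is lowest when they straddle 50% and rises towards 0% or 100%. A claim that power is at least some figure for a 15- or 20-point difference, whichever two doses are compared, therefore needs the least favourable rates, or a stated restriction on the rates. The plan gives neither. It computes at two pairs that share 80% as the higher rate, labels them examples, and attaches the result to all dose pairs.

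If one dose reaches 80% and the other two do not, two of the three pairwise comparisons include the 80% dose and one does not. That third comparison falls within the claim but outside the calculation. A reader who takes the floor literally would put the chance of missing a true difference at no more than 26% (15 points) or 5% (20 points). At the least favourable rates it is about 36% and 12%.

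**Working it through.** **Inputs**
- Evaluable infants per dose: 150 × 0.9 = 135. The 150 is 12 from Group C plus 138 from Group D. Section 4.1.1 gives it as "150 vaccine recipients per dose group and 450 vaccine recipients for the three dose groups combined".
- Allocation between doses: equal. Section 3.3.4 assigns Group D to the three doses "or to Placebo in a 1:1:1:1 ratio".
- Test: Fisher's exact, two-tailed, as named in section 4.1.1.
- Significance level: 0.05 two-sided, from the general rule in section 7. The power sentence does not repeat it.
- Rates: 65% vs 80% and 60% vs 80% are the plan's. All other pairs below are assumptions, run to show how the power varies.

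**Formula**

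Power = Σₓ Σᵧ Bin(x; 135, p₁) · Bin(y; 135, p₂) · 1[Fisher p(x, y) ≤ 0.05], summed over every possible pair of responder counts.

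**The plan's own examples first**
- 65% vs 80%: 75.3%, against a stated minimum of 74%. The claim is met.
- 60% vs 80%: 93.9%, against a stated minimum of 95%. The claim is missed by 1.1 points.

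A normal approximation without continuity correction does reach 95% at 60% vs 80%:
- SE under the null = √(2 × 0.70 × 0.30 / 135) = 0.0558
- SE under the alternative = √((0.60 × 0.40 + 0.80 × 0.20) / 135) = 0.0544
- z = (0.20 − 1.96 × 0.0558) / 0.0544 ≈ 1.67, so power ≈ 95.2%

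That is not the test the plan names. For 65% vs 80% the same approximation gives 79.2%.

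**Across other rates (135 per dose)**

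| Difference | Rates | Fisher exact | Uncorrected approximation |
|---|---|---|---|
| 15 points | 80 vs 95 | 96.2% | 96.5% |
| 15 points | 70 vs 85 | 81.0% | 84.3% |
| 15 points | 65 vs 80 (plan) | 75.3% | 79.2% |
| 15 points | 60 vs 75 | 71.2% | 75.2% |
| 15 points | 50 vs 65 | 66.9% | 70.5% |
| 15 points | 42.5 vs 57.5 (minimum) | 63.7% | 69.5% |
| 20 points | 75 vs 95 | 99.7% | 99.7% |
| 20 points | 65 vs 85 | 96.1% | 97.0% |
| 20 points | 60 vs 80 (plan) | 93.9% | 95.2% |
| 20 points | 50 vs 70 | 90.7% | 92.3% |
| 20 points | 40 vs 60 (minimum) | 88.2% | 91.2% |

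On a grid of rates in half-point steps, Fisher power is below 74% for a 15-point difference when the lower rate is between about 22% and 63%. It is below 95% for a 20-point difference when the lower rate is between about 17.5% and 62.5%.

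**Sensitivity**
- Test: the uncorrected approximation also falls below 74% and 95% at mid-range rates (69.5% and 91.2%).
- Sample size: with no loss at all (150 per dose), Fisher power is 80.3% and 96.0% at the plan's pairs, but still only 72.1% and 92.9% for rates centred on 50%.

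**The case against.** The strongest defence is that the power sentence directly follows the premise of 80% or more for at least one dose, and both examples use 80% as the higher rate. When the better dose of a pair is at 80% or above, 80% is the least favourable case, because power only rises from there (81.0% at 70% vs 85%, 96.1% at 65% vs 85%). Read with that premise, 74% is a true floor for any pair containing such a dose, and 95% is about one point too high at the boundary. This stands, and it limits the point. It does not cover the pair made up of the other two doses, which the wording includes and for which the plan fixes no rate.

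Three stronger readings are tempting, and the SAP does not support them:
- **That the examples were chosen to flatter the design.** Power is well above the example values at higher rates, so these are not the most favourable pairs. Under the stated premise they are the least favourable.
- **That the plan itself designs for rates near 60% or below in these comparisons.** The primary hypothesis does speak of a response "in 60% or more of participants in at least one of the study groups", but that concerns neutralizing responses to two or more of the three strains. The power sentence rests on strain-specific seroresponse. Nothing in the SAP names 45% vs 60% or 40% vs 60% as planning rates.
- **That choice of dose hangs on these tests.** Sections 5.8 and 7 base Phase 3 dose selection on all immunogenicity endpoints together with safety. The GMT comparison has its own power statement of 98%, and exact confidence intervals are planned for each response rate.

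**Conclusion.** The statement is wrong as worded, by a modest amount. At the plan's own rates one figure holds (75.3% against 74%) and the other falls about one point short (93.9% against 95%). As a general minimum for any two doses, neither holds. The true minimums are about 64% and 88%, so the overstatement is at most about 10 and 7 points, and it is smaller the closer the higher rate is to 80%.

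This rests on 135 evaluable infants per dose, a two-sided 0.05 level and the Fisher test the plan names. The fault is mainly one of scope. A reader might infer that the study delivers only 64% and 88% at its planning rates, or that it is too small. Neither follows, because those values apply only to rates centred on 50%, which the plan does not predict.

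**What to change.** Replace the sentence in section 4.1.1 with wording such as: with 135 evaluable infants per dose, the two-tailed Fisher's exact test at 0.05 has about 75% and 94% power for 65% vs 80% and 60% vs 80%; power is lower when both rates are below 80%, falling to about 64% and 88% for 15- and 20-point differences centred on 50%. Drop *at least* as a general claim for any two doses.

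The cost is one sentence. The stated figures become slightly less favourable. Enrolment, tests, populations and estimates stay as they are.
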